7.2.5. Reporting procedure for Suspected Unexpected Serious Adverse Events

Any SAEs that fulfil the definition of a SUSAR will be reported to the Competent Authority, - the Medicines and Health care products Regulatory Agency (MHRA) (if the SUSAR is related to the IMP/placebo), Research Ethics Committee (REC) and sponsor within 7 calendar days of the trial management team in the Trial Office becoming aware of the event if it resulted in death or was life threatening, or 15 calendar days for any other event. Treatment allocation will be unblinded prior to SUSAR reporting.

7.2.6. Development Safety Update Reports

The CI will submit (in addition to the expedited reporting above) DSURs once a year throughout the clinical trial, or on request, to the Competent Authority (MHRA in the UK), Ethics Committee, HRA (where required), and Sponsor.

7.3. Pregnancy

The manufacturer advises women of child-bearing potential to follow adequate contraceptive precautions for 5 months after the last injection. A woman of child bearing potential is defined as a premenopausal female capable of becoming pregnant. The SmPC states that a large number (approx. 1500) of pregnancies exposed to adalimumab in the first trimester does not indicate an increase in the rate of malformation in the newborn, however all females of child bearing potential will be asked if there is a possibility that they could be pregnant as part of the eligibility assessment before being randomised to the study. If there is a possibility they could be pregnant they will be offered a pregnancy test to confirm that they are not pregnant. If they refuse to take a pregnancy test they would be deemed ineligible. If pregnancy does occur in study participants treated with adalimumab – there is a potential for these infants to be at an increased risk of infection as adalimumab may cross the placenta into the serum of infants born to women treated with adalimumab during pregnancy. Administration of live vaccines (e.g. BCG vaccine) to infants exposed to adalimumab in utero is not recommended for 5 months following the mother's last adalimumab injection during pregnancy.

In the occurrence of pregnancy in a trial participant, no further doses of adalimumab are to be given, and the pregnancy must be reported as soon as the trial team are made aware to the Anti Freaze-F Trial team via completion of the Anti-Freaze-F Pregnancy Notification Form which must be emailed to [contact]. Alternatively, site can complete the electronic Pregnancy Notification Form via REDCap. The pregnancy must be followed up by the investigator until delivery for congenital abnormality or birth defect, at which point it would fall within the definition of a serious adverse event.

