4.3. INTERVENTIONS

4.3.1. Adalimumab/Placebo Injection

Eligible participants will be allocated to receive either an intra-articular injection of adalimumab (160mg in 3.2ml for the first injection, 80mg in 1.6ml for second injection) or placebo (normal saline [0.9% NaCl] 3.2ml for the first injection and 1.6ml for the second injection). The dose of 160mg followed by 80mg two weeks later was selected as this is the approved loading dose in patients with inflammatory bowel disease. The shoulder joint capsule is vascular and we anticipate that absorption into the blood stream will follow similar kinetics as when the adalimumab is administered subcutaneously. The injection will be given into the anterior shoulder joint space in the rotator cuff interval where there is maximal inflammation of the capsule and synovium, under guided ultrasound. The injection treatment is to be given within ideally 2 weeks after randomisation by an appropriately qualified practitioner, with experience of treating frozen shoulder by ultrasound guided injection who is appropriately delegated to do so. The practitioner will be either a GP with a specialist interest in musculoskeletal conditions, rheumatologist, extended scope physiotherapist, orthopaedic surgeon, sonographer or radiologist, dependant on the local service provision at site. The practitioner will need to confirm that the participant is still in the pain predominant phase before administering the first injection. If the practitioner deems that the participant is no longer in the pain predominant phase, the participant will not receive the injection and the reason will be recorded on the trial specific injection treatment log; the participant will still be included in the 3-month follow up assessment.

If a participant has symptoms of COVID-19, tests positive for COVID-19 or is self-isolating due to government guidelines and is unable to attend for either injection, the visit will be delayed until they

receive confirmation of a negative test result or have recovered as long as they remain in the pain predominant stage. If a participant is no longer considered to be in the pain predominant stage and is unable to have the injections this will be recorded on the injection CRF and will be recorded as a withdrawn from treatment but they will continue to be followed up at 3 months.

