4.5. PARTICIPANT TIMELINE

TIMEPOINT (post randomisation unless stated otherwise)	Screening	0-2 weeks	4-5 weeks	3 month follow up
ENROLLMENT:				
Screening log	✓			
Informed consent	✓			
Eligibility confirmed	✓			
Randomisation	✓			
INTERVENTIONS:				
1 st Anti-TNF/placebo injection		✓		
Physiotherapy advice leaflet provision	✓			
2 nd Anti- TNF/placebo injection			✓ ¹	
ASSESSMENTS:				
Serological testing e.g. TB ELISpot, Hepatitis B surface antigen		✓		
Pregnancy testing (if needed)	✓			
Baseline questionnaire	✓			
ROM Assessment	✓			✓
Follow-up questionnaire				✓
Follow-up clinic visit				✓
Qualitative interview (optional)				✓* within 4 weeks of intervention delivery
AE Reporting (grade 3 or above)	✓	✓	✓	✓

1. The second injection must be 2-3 weeks after the 1st injection.

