10.2. APPENDIX 2: SCHEDULE OF PROCEDURES

Activity	Screening	Visit 1 (injection 1)	Visit 2 (2 nd injection)	3 month Follow Up	Qualitative sub-study – optional participation
Diagnosis of pain-predominant frozen shoulder	✓				
Assessment of eligibility for trial	✓				
pregnancy test (if applicable)	✓				
Informed consent	✓				
Blood sample for serological testing for latent TB and Hepatitis B surface antigen		✓			
Completion of questionnaires	✓			✓	
Shoulder range of movement	✓			✓	
Randomisation	✓				
Physiotherapy advice leaflet	✓				
Injection of local anaesthetic		✓	✓		
Injection of adalimumab/placebo under guided ultrasound		✓	✓		
Assessment of AEs (grade 3 or above)	✓	✓	✓	✓	
Qualitative sub-study: telephone interview (optional)					✓✓* within 4 weeks of 1 st intervention delivery

10.3: APPENDIX 3: AMENDMENT HISTORY

Amendment no.	Protocol version no.	Date issued	Author(s) of changes	Details of changes made
6	V3.0	DDMMYYYY	[name]	
Amended the time frame of inclusion criteria to more accurately reflect the period of pain predominant early stage frozen shoulder of 3 to 9 months.
 
Added the Participant Range of Movement CRF
 
Amended the description of the needle gauge from 18 to 21
 
Added sentences to reflect the trial presence on social media and its aim of being present on publicly available web-platforms.
 
Added that sites will use SIMS to download completed eConsent Forms for filing.
 
Added that sites can complete an electronic Pregnancy Notification Form via REDCap.

				
Added that SAEs should be reported by sites via the electronic form on REDCap and that a paper form is available if necessary and should be emailed to the trial office.
 
Typographical errors and omissions corrected.

--	--	--	--	--

Protocol amendments will be submitted to the sponsor for approval prior to submission to the HRA, REC and MHRA.

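### The abstinence footnote in 7.3.1 sets 120 days where the contraception rule is 5 months, and no pregnancy check is scheduled before the second injection

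*Combined protocol and SAP*

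**What the plan says.** **Duration of contraception.** The inclusion criteria (4.2.1) ask women of child-bearing potential to use effective contraception during treatment and for 5 months afterwards. Section 7.3 gives the same 5 months and attributes it to the manufacturer. The second footnote in 7.3.1 accepts abstinence only if it lasts for the whole period at risk, and gives that period as 120 days after the final dose.

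**Detection of pregnancy.** Section 7.3 says of these same women that they "will be asked if there is a possibility that they could be pregnant as part of the eligibility assessment before being randomised to the study". A test is offered only if the answer is that pregnancy is possible. The participant timeline (4.5) and Appendix 2 both place the test at Screening and nowhere else.

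**Dosing.** Section 7.3 is explicit: "In the occurrence of pregnancy in a trial participant, no further doses of adalimumab are to be given, and the pregnancy must be reported". On timing, "The second injection must be 2-3 weeks after the 1st injection". Section 4.3.1 gives the second injection to everyone who does not decline it. Its reasons for withholding are a related adverse event of grade 3 or above, or a positive test for TB or hepatitis B surface antigen. Pregnancy is not in that list.

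**Outcome of pregnancy.** "The pregnancy must be followed up by the investigator until delivery for congenital abnormality or birth defect", and 7.3 adds that such a finding meets the definition of a serious adverse event. Section 7.2.4 asks sites to report only related SAEs, up to 28 days after the last injection.

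**The concern.** A participant who relies on abstinence falls under two durations that cannot both be right. The shorter one stands in the section that defines adequate contraception, which is where site staff would look it up.

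The dosing bar in 7.3 works only if somebody knows of the pregnancy. Between Screening and the second injection no step asks about it. The injection visits already include other checks. At the first, "The practitioner will need to confirm that the participant is still in the pain predominant phase before administering the first injection", and blood is taken for TB and hepatitis B. At the second, the clinician asks about adverse events attributed to the first injection. A pregnancy question would fit either visit, but neither has one. A practitioner working from 4.3.1 alone would not meet the pregnancy bar at all.

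At stake is a second dose of 80 mg given to a woman in an early pregnancy that one question might have brought to light. Section 7.3 names a potential infection risk for infants exposed in utero. None of this touches the feasibility outcomes, the analysis or the progression criteria.

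**Working it through.** The plan offers no calculation to reproduce here. The check is a comparison of the text, with calendar arithmetic.

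**1. 120 days against 5 months**

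- Inputs: 5 months (4.2.1 and 7.3); 120 days (7.3.1, second footnote).
- Five calendar months, counted from every start date over two years, last 150 to 153 days.
- Shortfall: 150 − 120 = 30 days, to 153 − 120 = 33 days.
- Share of the 5-month period covered: 120/153 = 78%, to 120/150 = 80%.

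Pharmacological size, using the 2-week half-life in 3.1.3 (Choice of comparators) and assuming simple exponential decline after the last dose:

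| Time after last dose | Half-lives | Fraction remaining |
|---|---|---|
| 120 days | 120/14 = 8.57 | 0.5^8.57 = 0.26% |
| 5 months (152 days) | 152/14 = 10.9 | 0.5^10.9 = 0.05% |

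Both fractions are very small. The discrepancy is an error of instruction more than one of exposure.

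**2. Age of the pregnancy check at each injection**

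- Injection 1: ideally within 2 weeks of randomisation (4.3.1), so at weeks 0 to 2.
- Injection 2: 2 to 3 weeks after injection 1, so at week 0 + 2 = 2 to week 2 + 3 = 5. The column in the 4.5 timeline reads 4 to 5 weeks.
- Screening comes no later than randomisation, so these are minimum ages: at least 0 to 2 weeks at injection 1 and at least 2 to 5 weeks at injection 2.
- Section 4.3.1 allows either visit to be put back for COVID-19, which lengthens both intervals.

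On schedule, the check is recent at injection 1. It is least current at injection 2, which is where a repeat is worth most.

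**3. The SAE window and delivery**

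- Window closes 28 days (4 weeks) after the last injection: 2 + 4 = 6 to 5 + 4 = 9 weeks after randomisation.
- Assumption, not in the documents: conception at randomisation and term birth 38 weeks later.
- Birth then falls 38 − 9 = 29 to 38 − 6 = 32 weeks after the window closes.

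Most deliveries would fall after a 28-day window, so this shows only that the timing limit in 7.2.4 and the follow-up in 7.3 need to be read together.

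**The case against.** The case on the other side is substantial.

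- **The dosing bar has a trigger.** A reader might infer that it has none, or that the plan permits dosing in pregnancy. It does not. A known pregnancy triggers the bar in 7.3, and 6.1.3 lets the investigator withdraw a participant for any necessary reason. The silence of 4.3.1 does not override 7.3. What is missing is a scheduled prompt.
- **The repeat check is imperfect.** A woman using contraception and unaware of a pregnancy may answer no and go untested. That stands, and it limits the gain. A repeat at an on-time first injection adds little.
- **The risk is low.** Section 7.3 says that experience from about 1,500 first-trimester exposures "does not indicate an increase in the rate of malformation in the newborn". Contraception is required and randomisation is 1:1 to placebo. On the assumption above, a term birth would come 38 − 5 = 33 to 38 − 2 = 36 weeks after injection 2, beyond the 5-month (about 22-week) precaution on live vaccines for exposed infants.
- **The 120 days may never reach a participant.** The eligibility criterion is 5 months with no exception by method. A reader might infer that women relying on abstinence are told 120 days. The consent pages are not available, so this cannot be known. The contradiction inside the protocol remains.
- **Birth defects are not lost.** A reader might infer that they would go unreported. Section 7.2.4 concerns SAEs in a participant, and an infant's birth defect arguably lies outside it. Section 7.3 requires notification, follow-up to delivery and SAE classification. Section 7.2.5, on SUSARs, repeats no 28-day limit. The notification form and the trials unit's safety procedures are not available either. What is left is a missing cross-reference.

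**Conclusion.** Three items of unequal weight.

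1. **Wrong as written.** The 120 days in 7.3.1 contradicts the 5-month rule by 30 to 33 days. Little drug should remain at either time (about 0.26% against 0.05%, given the 2-week half-life and exponential decline), but a safety instruction should not contradict itself.
2. **A cheap improvement.** With the only check at least 2 to 5 weeks old at the second injection, detection depends on the participant volunteering a pregnancy. Repeating the question would support a rule that the plan already has. The gain is modest, and its size cannot be estimated because the documents do not say how many of the 84 participants are expected to be of child-bearing potential.
3. **Optional clarification.** The link between 7.2.4 and 7.3 could be stated. The documents do not show that a birth defect would escape reporting.

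**What to change.** - **7.3.1, second footnote:** replace 120 days with 5 months.
- **Before injection 2:** ask the existing pregnancy question, with a test if pregnancy is possible, before the product is prepared. Do the same before injection 1 if that visit is delayed. Mark this in the 4.5 timeline and in Appendix 2.
- **4.3.1:** add pregnancy to the reasons for withholding the second injection.
- **7.2.4 (optional):** add a sentence pointing to 7.3 and saying that a birth defect found at pregnancy follow-up is reported despite the 28-day and related-only limits.

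The cost is a question at a visit that already takes place, a few extra urine tests, some wording edits and a protocol amendment. Under 8.2, changes to study procedures or patient safety need a formal amendment, and a substantial one needs HRA, REC and/or MHRA approval, so the edits are best made together. No new visit, assessor or data system is needed, and the sample size and analysis do not change.

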7.3.1 Contraception

The following are considered adequate contraception for the purpose of this trial:

- combined (oestrogen and progestogen containing) hormonal contraception associated with inhibition of ovulation : oral, intravaginal, transdermal
- progestogen-only hormonal contraception associated with inhibition of ovulation : oral, injectable, implantable
- intrauterine device (IUD)

- intrauterine hormone-releasing system (IUS)
- bilateral tubal occlusion
- vasectomised partner ¹
- sexual abstinence ²

¹ Vasectomised partner is a highly effective birth control method provided that partner is the sole sexual partner of the WOCBP trial participant and that the vasectomised partner has received medical assessment of the surgical success.

² In the context of this guidance sexual abstinence is considered a highly effective method only if defined as refraining from heterosexual intercourse during the entire period of risk associated with the study treatments, in this trial – this is a 120 day period from the last dose of IMP.

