The palmar nodules in patients with Dupuytren's disease are readily identifiable clinically. However, the only means of accurately delivering adalimumab to the involved areas in patients with frozen shoulder is by ultrasound guidance. Furthermore, due to the larger area involved, we will use 160mg of adalimumab in 3.2ml. It is possible that some patients may fail to gain significant improvement in symptoms following administration of 160mg of adalimumab. The half-life of adalimumab is 2 weeks and up to 160mg can be administered as a loading dose in patients with inflammatory disorders such as Crohn's disease (<https://bnf.nice.org.uk/drug/adalimumab.html#indicationsAndDoses>). Patients will receive a second injection of adalimumab (80mg in 1.6ml) at 2-3 weeks after the initial injection.

We are not aware of any other trials for frozen shoulder investigating the efficacy of using a drug targeting a defined inflammatory cytokine. The anti-TNF drugs have a very strong safety profile, having been used in over 10 million people, adalimumab in over 5 million, and more than 25,000 patients have been recruited to trials of adalimumab, which is approved for 9 different disorders. In these, only 0.2% of patients with chronic inflammatory disorders discontinued long-term use of the drug, which is administered every 2 weeks, due to adverse effects. Anti-TNF drugs not routinely administered as an intra-articular injection, although there are a few reports of outcomes in patients with inflammatory or osteoarthritis (28-31). We are not aware of any trials where intra-articular injection of adalimumab has been used in people with frozen shoulder. Adalimumab is not currently licenced for use as an intra-articular injection for pain-predominant early-stage frozen shoulder and therefore will be used off license for the purposes of this trial. Therefore, as part of this feasibility trial we will also assess the safety of anti-TNF injection when given as an intra-articular injection, by recording any clinician reported grade 3 or above adverse events.

Administration of adalimumab should not pose any risks in relation to COVID-19 vaccinations or to patients who may have contracted COVID-19. None of the approved vaccines involve live viruses. Adalimumab was being trialled in UK care home residents for the treatment of COVID-19, although this trial has been closed because of the lack of eligible participants due to the success of the

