4.2.1. Inclusion criteria

We will include:

- Men and women aged 18 years and above;
- With a new episode of shoulder pain attributable to pain-predominant stage of frozen shoulder (i.e. within approximately 3 to 9 months of onset of symptoms) diagnosed using criteria set out in the BESS guidelines (35) (Appendix 1);
- Who are not being considered for surgery;
- Able to understand spoken and written English;
- Willing and able to give informed consent for trial participation and comply with all study requirements and time line;

- Willing to allow his or her General Practitioner be notified of participation in the trial.
- If female, and of child-bearing potential, willing to use effective contraception throughout the treatment period and for 5 months after the last injection. See section 7.3 and 7.3.1 for definitions.

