4.2.2. Exclusion criteria

We will exclude:

- Those with frozen shoulder secondary to significant shoulder trauma (e.g., dislocation, fracture or full thickness tear requiring surgery) or other causes (e.g. recent breast cancer surgery or radiotherapy);
- Those with a neurological disease affecting the shoulder;
- Those with bilateral early stage frozen shoulder;
- Those with other shoulder disorders (e.g., inflammatory arthritis, rotator cuff disorders, glenohumeral joint instability) or with red flags consistent with the criteria set out in the BESS guidelines (35);
- Those who have received corticosteroid injection for shoulder pain in the last 12 weeks to either shoulder;
- Those currently taking any anti-TNF drug;
- Those being treated with coumarin anticoagulants, such as warfarin;
- Those who have participated in another research study involving an investigational medicinal product in the past 12 weeks;
- Those with significant renal or hepatic impairment;
- Those with contra-indications to anti-TNF injection:
 - Known allergy to any anti-TNF agent or any of the excipients;
 - Known Active tuberculosis (TB) or history of TB or at risk of developing TB e.g. through the use of immunosuppressants (see below (3))
 - Known Active infection (chronic or localised) or known history of recurring infections or condition which may predispose patients to infection, including the use of concomitant immunosuppressive medications;
 - Known Moderate to severe heart failure (NYHA class III/IV);
 - Those known to have HIV, Hepatitis B or C;
 - Those at risk of Hepatitis B infection;

- Those diagnosed with Multiple Sclerosis (MS) or other central or peripheral nervous system demyelinating disorders;
- Those who have ever been diagnosed with cancer, except basal cell carcinoma (BCC);
- Those requiring live vaccination within 5 months of the last trial injection or within the 4 weeks prior to randomisation;
- Those taking biologic DMARDs;
- Females who are currently breastfeeding.
- Any other significant disease or disorder which, in the opinion of the Investigator, may either put the participants at risk because of participation in the study, or may influence the result of the study, or the participant's ability to participate in the study.

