4.3.5 Contraindicated medications

Concomitant administration of biologic DMARDs is contraindicated during the treatment period and until 4 months after the last injection. The use of live vaccines must also be avoided until 12 weeks after the last injection.

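### Footnote 2 of section 7.3.1 sets the abstinence period at 120 days after the last dose, 30–33 days short of the 5 months required by 4.2.1 and given in 7.3

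*Combined protocol and SAP*

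**What the plan says.** Three places in the current protocol text bear on this point.

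- **4.2.1, Inclusion criteria.** A woman of child-bearing potential must be "willing to use effective contraception throughout the treatment period and for 5 months after the last injection. See section 7.3 and 7.3.1 for definitions".
- **7.3, Pregnancy.** The section opens with the same period: "The manufacturer advises women of child-bearing potential to follow adequate contraceptive precautions for 5 months after the last injection".
- **7.3.1, Contraception.** This lists the accepted methods. Footnote 2 accepts abstinence only when it means "refraining from heterosexual intercourse during the entire period of risk associated with the study treatments", and then puts a number on that period: "this is a 120 day period from the last dose of IMP".

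Abstinence is the only method in the list with a duration attached. The footnote on a vasectomised partner sets conditions but no period. The protocol does not explain why the abstinence period differs from the 5 months.

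**The concern.** The inclusion criterion has a safety purpose, and one of the two sections it cites for definitions contradicts its duration. The footnote does not present 120 days as a minimum or as a special case. It equates 120 days with the full risk period, so on its face it tells a site when the need for abstinence ends.

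What is at stake is pregnancy in the weeks between the two periods. Section 7.3 gives the reason for caution: adalimumab may cross the placenta, and exposed infants may be at increased risk of infection. A site that counsels from the footnote would release a woman relying on abstinence before the period in 4.2.1 and 7.3 has run. As the working shows, no planned visit remains by then at which the error could be corrected.

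**Working it through.** **Inputs**

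- Abstinence period: 120 days from the last dose (7.3.1, footnote 2).
- Required contraception period: 5 months after the last injection (4.2.1; repeated as manufacturer's advice in 7.3).
- Half-life: "The half-life of adalimumab is 2 weeks" (3.1.3, Choice of comparators), i.e. 14 days.
- Schedule: first injection 0–2 weeks after randomisation, second injection 2–3 weeks after the first (4.5); follow-up 3 months after randomisation (6.1.2).

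The protocol gives no derivation for the 120 days, so there is nothing to reproduce.

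**Step 1: 5 months in days.** Over all start dates in 2022–2024, 5 calendar months ranges from 150 to 153 days.

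- Shortest, for example 1 February to 1 July in a non-leap year: 28 + 31 + 30 + 31 + 30 = 150.
- Longest, for example 1 March to 1 August: 31 + 30 + 31 + 30 + 31 = 153.

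**Step 2: the gap.** 150 − 120 = 30 and 153 − 120 = 33, so the footnote is 30–33 days short. Four calendar months is 120–123 days, so 120 days corresponds to 4 months and not to 5.

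**Step 3: where this falls in the schedule.** Take 3 months as about 13 weeks. The second injection falls between week 0 + 2 = 2 and week 2 + 3 = 5 after randomisation. The follow-up visit is then 13 − 5 = 8 to 13 − 2 = 11 weeks after the last injection, or 56–77 days, and sooner if injections are delayed. Both 120 days and 5 months lie beyond it.

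**Step 4: scale of exposure.** This step assumes simple first-order decline from the last injection. The fraction remaining at day *d* is 2^(−*d*/14).

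| Days after last dose | Half-lives | Fraction remaining |
|---|---|---|
| 120 | 8.6 | 0.26% |
| 150 | 10.7 | 0.06% |
| 153 | 10.9 | 0.05% |

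The difference is small. The protocol does not use half-lives to justify either period, so this gives a sense of scale and does not settle which period is right.

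**Step 5: how many are affected.** The documents do not say how many of the 84 participants will be women of child-bearing potential or will rely on abstinence. With 1:1 allocation, 84/2 = 42 would be assigned adalimumab. The number affected is some unknown part of that.

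**The case against.** The strongest reply is that 4.2.1 states the duration outright and defers to the later sections only for definitions. A woman who stops abstaining at day 120 would still be bound by 4.2.1 to use another listed method until 5 months. The reference in 4.2.1 is also to 7.3 as well as 7.3.1, and 7.3 opens with 5 months, so a site reading in order meets the right period twice before it reaches the footnote. This stands in large part. A reader might infer that the criterion hands its duration over to the footnote, or that 120 days is the operative rule. The documents do not support that. They support only that one footnote contradicts the rule it is meant to serve.

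Other mitigating points also stand. Section 7.3 cites about 1500 first-trimester exposures with no signal of more malformations, and requires any pregnancy to be reported and followed to delivery. The participant materials are not in the file and may already say 5 months, so it is an assumption that anyone would be counselled from the footnote.

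A reader might also want to add live vaccines as a second conflict. Section 4.2.2 excludes "Those requiring live vaccination within 5 months of the last trial injection or within the 4 weeks prior to randomisation", while 4.3.5 says: "The use of live vaccines must also be avoided until 12 weeks after the last injection". The documents do not support calling this an inconsistency. The first is an entry screen for a foreseen need and the second a rule on use after dosing, and both can be obeyed. Section 4.3.5 also sets a separate period of 4 months for biologic DMARDs, so different periods may be deliberate. Nothing in the file settles the right period for adult vaccination. At most it is a separate query to the sponsor.

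What the reply does not remove is the footnote's own claim that 120 days is the whole risk period. That claim disagrees with 4.2.1 and 7.3, and nothing in the protocol reconciles them.

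**Conclusion.** The discrepancy is real. Footnote 2 of 7.3.1 is wrong as written against 4.2.1 and 7.3, by 30–33 days. It affects only women who rely on abstinence, and only if they are counselled from the footnote. The day count rests on calendar arithmetic alone; the exposure figures rest on the protocol's half-life and an assumed first-order decline.

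No harm is shown, and a reader should not infer one: the estimated difference in remaining drug is small and the number of women concerned is unknown. The sample size, the analysis and the progression criteria in Table 4 are untouched. This is a minor safety-wording correction, justified because the protocol should give one period, consistent with the manufacturer's advice that it cites.

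**What to change.** In footnote 2 of 7.3.1, replace the 120-day period with: *the treatment period and 5 months after the last dose of IMP*. This matches 4.2.1 at both ends, since the present footnote counts only from the last dose. Then check that the participant information sheet, the post-injection leaflet, the laminated card and the site training give the same period wherever they mention one.

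The cost is one phrase in a protocol amendment and a document check. Abstinence would last 30–33 days longer than the footnote now says, but no longer than 4.2.1 already requires.
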